4.2.1.6. Concomitant treatments

The anatomical therapeutic chemical classification (ATC code = 5 digits) is composed of 4 levels:

- The first (1 digit) represents the anatomo-physiological class.
- The second (2 digits) represents the pharmacological class.
- The third (1 digit) represents the pharmacological sub-class.
- The last (1 digit) represents the therapeutic class.

The existence of a concomitant treatment (Yes/No) is defined from the presence, or not, of an ATC classification and/or preferred name.

The **periods** considered for the analysis are:

During the study period, for which the concomitant treatment:

- LIDstart date \geq LIDinclusion date
- start date < inclusion date LIDand stop date \geq LIDinclusion date or missing

At inclusion and before the treatment period, for which the concomitant treatment for tumour lysis syndrome prevention:

- start date < first S64315 infusion date (during the LID period) , or
- start date \leq inclusion date and stop date \geq inclusion date or is missing

The following **rules for substitution** of missing or incomplete start and stop dates are so that the concomitance period is maximised:

Table (4.2.1.6) 1 - Substitution rules of concomitant treatments intake dates

Date to substitute	Substituted date
Start date ../mmm/yyyy	If the year and the month are the same as the year and the month of inclusion, then Start date= Inclusion date , otherwise Start date= 01/mm/yyyy
Start date ../.../yyyy	If the year is the same as the year of inclusion, then Start date= Inclusion date , otherwise Start date= 01/01/yyyy
Stop date ../.../....	If stop date is non-missing and inferior to inclusion date, then: Stop date Else: Inclusion date
Stop date ../mmm/yyyy	If patient died same month and year, then Date of death Else Last day of the month/mmm/yyyy
Stop date ../.../yyyy	If patient died same year, then Date of death Else 31/DEC/yyyy
Stop date ../.../....	If patient died, then Date of death Else No substitution (i.e., treatment considered as still ongoing)

Note: ../mm/yyyy = missing day
 ../.../yyyy = missing day and month
 ../.../.... = missing date

The following rules for substitution of totally or partially missing start and stop dates are used for concomitant treatments (only further anti-leukemic therapy):

S 64315

CL1-64315-004 – Statistical Analysis Plan – Final V1.0

Table (4.2.1.6) 2 - Substitution rules of further anti-leukemic therapy intake dates

	Date to substitute	Substituted date
	../mmm/yyyy	If the year and the month are the same as the year and the month of the last IMP intake date, then Last IMP intake date otherwise 01/mm/yyyy
Start date	../.../yyyy	If the year is the same as the year of the last IMP intake date, then Last IMP intake date, otherwise 01/01/yyyy
	../.../....	Last IMP intake date
	../mmm/yyyy	If patient died same month and year, then Date of death Else Last day of the month/mmm/yyyy ,
Stop date	../.../yyyy	If patient died same year, then Date of death Else 31/DEC/yyyy
	../.../....	If patient died, then Date of death Else No substitution (i.e., treatment considered as still ongoing)

Note: ../mm/yyyy = missing day
 ../.../yyyy = missing day and month
 ../.../.... = completely missing date

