1.2. Study endpoints

The endpoints for the primary objective are:

- The incidence of DLT(s) starting from the lead-in dose (LID) period to the end of each cycle of treatment of S64315 in combination with azacitidine.
- The incidence and severity of adverse events (AEs) and serious adverse events (SAEs) according to the National Cancer Institute Common Terminology Criteria for Adverse Events (NCI-CTCAE) version 5.0.
- The recording of any change or addition of a new concomitant treatment.
- The laboratory tests: haematology with differential, blood biochemistry, thyroid function, blood coagulation, urinary analysis, hepatitis markers, Tumour Lysis Syndrome (TLS) monitoring, cardiac markers follow up.
- The complete physical examination, Eastern Cooperative Oncology Group (ECOG) performance status and vital signs measurements.
- The electrocardiogram (ECG) parameters and cardiac function assessment.
- The left ventricular ejection fraction (LVEF).
- The dose interruptions, reductions and dose intensity.

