3.2.4.13. TLS prevention

All concomitant treatments for TLS prevention taken at inclusion and before the treatment period will be described for each dose level combination and overall in the SS, by Anatomical Therapeutic Chemical (ATC) code into 4 levels (Pharmacological class, Pharmacological subclass, therapeutic class, Preferred name). TLS risk category, type of hydration performed and anti-hyperuricaemic administration will also be presented.

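### Two date rules in SAP 4.2.1.6 count drugs known to have stopped before inclusion: partial start dates move to inclusion unchecked, and the TLS-prevention window has no effective stop-date condition

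*SAP*

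**What the plan says.** SAP 4.2.1.6 defines which treatments count as concomitant and how incomplete dates are filled.

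- **Start with day missing:** "If the year and the month are the same as the year and the month of inclusion, then Start date= Inclusion date".
- **Start with day and month missing:** "If the year is the same as the year of inclusion, then Start date= Inclusion date".
- **Date totally missing:** "If stop date is non-missing and inferior to inclusion date, then: Stop date"; otherwise the inclusion date. This is the only row with a stop-date check. It is printed beside a stop-date label, but its content fits only a missing start, and another row already covers a totally missing stop.
- **Study period:** a treatment qualifies if its start is on or after inclusion, with no further condition. If its start is earlier, its stop must be on or after inclusion, or missing.
- **TLS prevention:** a treatment qualifies under "start date < first S64315 infusion date (during the LID period) , or" a second branch, which asks for a start no later than inclusion together with a stop no earlier than inclusion, or missing.

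The substitution rules are stated to aim at the longest possible concomitance. They feed two Safety Set tables: concomitant treatments (SAP 3.2.5.2) and "All concomitant treatments for TLS prevention taken at inclusion and before the treatment period" (SAP 3.2.4.13). SAP 4.2.1.4 identifies the TLS drugs by a code list and states no date or indication filter.

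**The concern.** The second study-period condition shows that treatments finished before inclusion are meant to be left out. The two partial-start rows defeat this. Once the start has been moved to inclusion, the first condition is met and the stop date is never consulted. The derived record has a start after its stop, and the treatment is tabulated as taken during the study.

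The TLS rule has a similar gap and does not need an incomplete date. Its first branch stands alone and has no stop-date condition, so a course of a listed drug that ended well before inclusion is tabulated as TLS prevention in this trial.

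Such records are possible. The protocol collects previous as well as concomitant treatments at screening (Sections 8.2 and 8.2.1) and requires several drug classes to be stopped before the first IMP administration (Sections 5.4.2, 6.3 and 6.3.1). At stake is the accuracy of two descriptive tables and the internal consistency of the analysis dataset.

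**Working it through.** The plan gives no figure to reproduce; the check applies the rules as written.

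**Partial start dates.** Illustrative dates: inclusion 20 March 2021, first S64315 infusion 24 March 2021.

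| Recorded start | Recorded stop | Derived start | In study-period table? |
|---|---|---|---|
| 2 Mar 2021 (complete) | 10 Mar 2021 | 2 Mar 2021 | No |
| Mar 2021, day missing | 10 Mar 2021 | 20 Mar 2021 | Yes, start after stop |
| 2021, day and month missing | 15 Jan 2021 | 20 Mar 2021 | Yes, start after stop |
| Totally missing | 15 Jan 2021 | 15 Jan 2021 | No |
| Feb 2021, day missing | 10 Feb 2021 | 1 Feb 2021 | No |

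A partly known start is therefore misclassified where a totally unknown one is not. The last row shows the limit of the fault: the start must fall in the inclusion month (day missing) or the inclusion year (day and month missing).

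The longest gap between the known stop and inclusion that can still be misclassified is:

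- day missing: stop on the 1st, inclusion on the 31st, 31 − 1 = 30 days;
- day and month missing: stop on 1 January, inclusion on 31 December, 365 − 1 = 364 days (365 in a leap year).

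The rules were also run on an artificial grid: inclusion on each of 365 days, stop 1 to 90 days earlier, and four course lengths, so 365 × 90 × 4 = 131,400 records per type of start date. All of these drugs truly stopped before inclusion.

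| Start date | Counted as concomitant | Share | After the fix |
|---|---|---|---|
| Complete | 0 | 0% | 0 |
| Day missing | 10,535 | 8.0% | 0 |
| Day and month missing | 110,700 | 84.2% | 0 |
| Totally missing | 0 | 0% | 0 |

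Every misclassified record had its derived start after its stop. The shares depend on the chosen grid. They test the logic and do not estimate the trial's error rate.

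**TLS window.** Let s be the start, e the stop, I inclusion and F the first infusion. SAP 1.3.2 puts inclusion up to 15 days before the LID period, so I ≤ F.

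- Branch 1: s < F.
- Branch 2: s ≤ I, and e ≥ I or missing.
- Branch 2 adds a record only if s ≥ F and s ≤ I. With I ≤ F this forces s = I = F.

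Enumeration over gaps of 0 to 15 days agrees: of 81,360 combinations, branch 2 adds 41, all with start, inclusion and first infusion on one day. The stop-date test therefore has almost no effect. A listed drug taken from 1 January to 30 June 2018 is counted for an inclusion on 20 March 2021. With a stop on or after inclusion required, it is not.

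**The case against.** The best defence of the partial-date rows is their stated aim of maximising concomitance. That aim justifies resolving uncertainty towards inclusion in the table. It does not reach a recorded stop before inclusion, where no uncertainty remains, and the table's own stop-date check respects such a stop.

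Exposure is also uncertain. Protocol 6.3.3 asks for medications given during the study, previous AML or MDS drugs have their own eCRF page (SAP 4.2.1.3.5), and no look-back is stated for other previous treatments. Few affected records may exist. This limits the importance but does not make the rules right.

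Section 4.2.1.6 also contains stray text in the period rules, and the row with the stop-date check has to be read as a missing start. The comparison with that row rests on this reading. The missing check in the two partial-start rows does not.

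A reader might infer more than the documents support:

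- **That drugs stopped between inclusion and the first infusion are misclassified.** SAP 3.2.5.2 tabulates treatments during the study period, which 4.2.1.6 starts at inclusion. Counting them is by design, and the table does not claim that they were taken together with S64315.
- **That every anti-hyperuricaemic course ended before LID1 is wrongly counted.** SAP 3.2.4.13 covers treatments before the treatment period, so a course given between inclusion and LID1 belongs there. Only courses ended before inclusion do not.
- **That the TLS outputs cannot show whether prophylaxis was in place.** SAP 3.2.4.13 also presents risk category, type of hydration and anti-hyperuricaemic administration.
- **That the table must separate new from ongoing treatments** because SAP 1.2 lists "The recording of any change or addition of a new concomitant treatment". A flag for new treatments would be a refinement; its absence is not an error in the date rules.

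**Conclusion.** Both faults stand on the text, with the boundary at inclusion. A treatment with a known stop before inclusion and a partial start in the inclusion month or year is given an impossible start and is counted in the study period. A listed TLS drug that ended before inclusion is counted whether or not its dates are complete.

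The consequence is minor. It is confined to the descriptive Safety Set tables of concomitant treatments and TLS prevention. The DLT, MTD and adverse-event analyses do not use these rules. The number of affected records cannot be found in the documents. The TLS result assumes that inclusion is never later than the first infusion, as the study plan in SAP 1.3.2 implies.

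**What to change.** Make two changes in SAP 4.2.1.6.

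1. In both partial-start rows, put first: if the stop date is non-missing and earlier than inclusion, the start date equals the stop date. This is the check that the table already has for a totally missing date.
2. For TLS prevention, require a start before the first S64315 infusion **and** a stop on or after inclusion, or missing. If a drug started on a day that is both inclusion and first infusion should still count, keep the present second branch beside this condition.

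The study-period start can stay at inclusion. The label of the row holding the existing check should be corrected to the start date at the same time. The cost is a few lines of SAP text and the matching derivation conditions, with no new data and no change to any other analysis.

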4.2.1.7. Other observations related to patient follow-up

N.A.

4.2.2. Efficacy

N.A.

4.2.3. Safety**4.2.3.1. Dose Limiting Toxicity (DLT)**

A DLT is defined as:

- A clinically significant adverse event graded according to the NCI-CTCAE version 5.0, observed following the administration of the test drugs.
- Assessed as unrelated to disease progression, intercurrent illness, or concomitant Medications.
- At least possibly related to the test drug(s) by the investigator and meeting any of the criteria included in [Table \(4.2.3.1\) 1](#).

DLT will be reported based on investigator, using the ‘Dose limiting toxicity (DLT)’ / ‘Adverse event’ e-CRF page, and not recalculated.

Table (4.2.3.1) 1 –Toxicity criteria

TOXICITY	DLT CRITERIA
Eye disorders: blurred vision; cataract; corneal ulcer; dry eye; eye pain	Grade ≥ 3 confirmed by an ophthalmologic examination
GI disorders	Grade ≥ 3 nausea, vomiting or diarrhoea resulting in hospitalization, tube-feeding or use of total parenteral nutrition (TPN) Grade 4 diarrhoea
Renal abnormalities	Grade ≥ 3 serum creatinine
Hepatic abnormalities	AST or ALT ≥ 3 xULN along with a total bilirubin > 2.0 xULN and confirmed Hy’s law cases according to FDA guidance; For patients with elevated baseline AST or ALT or total bilirubin: [AST or ALT > 2.0 xbaseline AND > 3.0 xULN] OR [AST or ALT > 8.0 xULN], whichever is lower, combined with [total bilirubin > 2.0 x baseline AND > 2.0 xULN] Isolated Grade 3 AST or ALT which does not resolve within 7 days to Grade ≤ 1 Isolated Grade 4 AST or ALT
For any Grade ≥ 3 hepatic toxicity which does not resolve within 7 days to Grade ≤ 1 level or baseline, an abdominal CT scan or hepatic echography must be performed.	
Pancreatic abnormalities	Grade ≥ 3 serum lipase and/or serum amylase Grade ≥ 3 pancreatitis
For any Grade 3 or Grade 4 pancreatic toxicity, which does not resolve within 7 days to Grade ≤ 1 level or baseline, an abdominal CT scan must be performed	
Creatine kinase (CK) / Creatine phosphokinase (CPK)	Grade ≥ 3 serum CK/CPK Grade 3 isolated electrolyte abnormalities (i.e. those occurring without clinical consequence) not recovered with or without intervention, to Grade < 2 level within 72 hours

Electrolyte abnormalities (including magnesium, calcium, phosphorus, etc.) clinically significant	Any Grade 4 electrolyte abnormality
Cardiac disorders	
QTcF interval \geq 501 ms or increase of $>$ 60 ms from baseline on at least two separate ECG assessments (1 assessment = triplicate ECG)
 
Asymptomatic, absolute decrease in LVEF of 10% or greater from baseline AND LVEF $<$ 50%
 
Asymptomatic, absolute decrease in LVEF of 20% or greater from baseline
 
Troponin increase $>$ 10xULN or a troponin increase consistent with the diagnosis of a myocardial infarction (Grade 3)
 
Symptomatic congestive heart failure

Skin and subcutaneous tissue disorders	Grade \geq 3 rash
Haematological abnormalities	Grade 4 neutropenia and/or thrombocytopenia persisting for 28 days after the start of azacitidine dosing in a cycle of therapy in the absence of active AML ($<$ 5% blasts) or active MDS or myelofibrosis
Other AEs	
Any Grade \geq 3 AE
 
Single event or multiple occurrences of the same event that lead to a dosing delay of $>$ 7 days in a cycle may be considered to be DLT by the Investigators and the Sponsor, even if not Grade \geq 3
 
Failure to restart test drug administration at the same dose due to drug-related toxicity
 
Failure to restart test drug administration at the same dose within one cycle (i.e. 28 days) of the first missed dose due to delayed recovery from drug-related toxicity
 
Failure to initiate cycle 1 after completing the LID period or failure to receive LID2 after receiving the LID1, due to drug-related toxicity

NCI CTCAE v5.0 will be used for grading	

4.2.3.2. Adverse events

Each **medical concept of adverse events coded according to the internal "multiple medical concept" process** is taken into account as a single adverse event in the statistical analysis.

The modalities of the adverse event (onset and end dates, severity, seriousness, action taken, additional therapy, relationship, outcome...) replicated by default to each medical concept are also taken into account in the statistical analyses.

Emergent adverse events on treatment are defined as all adverse events:

- which occur between the first IMP intake date (included) and the last IMP intake date "+ (* days",

or

- which was present before the first IMP intake date and which worsen (in terms of severity) or become serious according to the investigator opinion between the first IMP intake date (included) and the last IMP intake date "+ (* days".

(*): 30 days for regimen QW.

Note: Adverse events occurring or worsening or becoming serious on the day of the first IMP intake (if any) is considered as emergent.

Serious adverse events are defined as all adverse events upgraded by the sponsor during the independent medical exam (IME) or PharmacoVigilance (PV) process (upgrade of seriousness) or considered as "serious" from investigator assessment.

Serious adverse events from investigator assessment are defined as all adverse events fulfilling at least one of the following seriousness criteria for immediate notification: death, hospitalisation, or prolongation of hospitalisation, medically important, life-threatening, disability/incapacity or congenital anomaly.

A fatal adverse event corresponds to an adverse event with “Fatal” as outcome.

Adverse events related to S64315 correspond to adverse events with relationship forced by the sponsor during the PV process (upgrade of relationship for adverse events assessed as serious according to investigator or sponsor opinion) or considered as "related" from investigator assessment. In other cases, the adverse events are considered as "not related to S64315".

Adverse events related to azacitidine correspond to adverse events with relationship considered as "related" from investigator assessment. In other cases, the adverse events are considered as "not related to azacitidine".

Adverse events related to S64315 and azacitidine from investigator assessment correspond to adverse events associated with the answer "Related" to the "Is this event related to S64315" question and “Related” to the “Is this event related to azacitidine” question.

The following information will be taken into account:

- For the analyses where the severity of the adverse event is considered, the worst severity from the day of emergence and during the studied period (i.e. between the first IMP intake date (included) and the last IMP intake date "(*) days" (included)) will be taken into account.
 - The number of patients by worst grade: for each patient, SOC and PT, we analyse the worst grade of events.
 - The number of events by worst grade: for each patient, SOC and PT, we analyse the worst grade of each event. The percentage will be calculated as the number of events of the PT concerned at grade X divided by the total number of events of the PT concerned.
 - For the analyses where the action taken regarding the IMP (S64315 and/or azacitidine) and the additional therapy requirement are considered, all the actions taken, and additional therapy requirements recorded from the day of emergence and on the studied period will be taken into account.
- However, in case of an episode of an emergent adverse event leading to studied treatment withdrawal reported after the last IMP intake date "+ (*) days", the adverse event will be considered as leading to studied treatment withdrawal during the studied period.
- Seriousness is judged by event: if one episode is serious (whatever the time it occurs), the whole event will be considered as serious.
 - A severe adverse event corresponds to an adverse event with NCI-CTCAE version 5.0 grade 3, 4 or 5.
 - Any grade corresponds to an adverse event with NCI-CTCAE version 5.0 grade 1, 2, 3, 4 or 5.
 - All multicoded events will be taken into account in the analyses.
 - For the analysis of recovered emergent adverse event during / after treatment period, a TEAE is considered as recovered “during treatment period” (“after end of treatment period”,

respectively) if the associated outcome is recovered” or “recovered with sequelae” and occurs between the first IMP intake date and the last IMP intake date “+ (*) days”(included) (strictly after the last IMP intake date “+ (*) days”, respectively).

(*): 30 days for regimen QW

The following rules are applied in case of missing severity:

Table (4.2.3.2) 1 – Emergence of adverse events in case of missing severity/grade (if any)

Severity/Grade		Adverse event considered as
Nearest before the first IMP intake date	During the study period	
Missing	Missing	→ Emergent
Missing	Grade 1	→ Non emergent
Missing	Grade 2, 3, 4 or 5	→ Emergent
Grade 1, 2, 3	Missing	→ Emergent
Grade 4	Missing	→ Non emergent

The rules for substitution of missing or incomplete episode date (onset date, dates of the six seriousness criteria and dates of change of severity and action taken) are as follows:

Table (4.2.3.2) 2 – Substitution rules of AE dates

Date to substitute	Substituted date (Episode date)
../mmm/yyyy	- If same month and year than first IMP intake date, then: First IMP intake date Else: 01/mmm/yyyy
- ../.../yyyy	- If same year than first IMP intake date, then: First IMP intake date Else: 01/JAN/yyyy
- ../.../....	- First IMP intake date

Notes:

../mm/yyyy = missing day.

../.../yyyy = missing day and month.

../.../.... = missing date.

The rules for substitution of missing or incomplete recovery dates, in case of AE outcome "recovered" "recovered with sequelae" are as follows:

Table (4.2.3.2) 3 - Substitution rules of recovery date

Date to substitute	Substituted date
../mmm/yyyy	If same month and year than date of AE last information ^(*) , then: Date of AE last information Else: Last day of the month /mmm/yyyy
../.../yyyy	If same year than date of AE last information ^(*) , then: Date of AE last information Else: 31/DEC/yyyy
../.../....	Date of AE last information*

Notes:

../mm/yyyy = missing day.
 ../.../yyyy = missing day and month.
 ../.../.... = missing date.

* Date of AE last information is defined as the maximum between onset date, dates of change of severity and action taken and dates of the six seriousness criteria for this adverse event.

Duration of AE (days): (recovery date (last episode) – onset date of AE) + 1.

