8.10. Responsibilities of the sponsor

In accordance with international guidance, the assessment of the seriousness and the causality of adverse events are usually made by the investigator but falls also under sponsor's duties, who is responsible for ensuring that all suspected unexpected serious adverse reactions are reported to Competent Authorities and Ethics Committees.

The sponsor will review the seriousness of the adverse events and the causality of (at least) the SAEs, whether reported by the investigator or upgraded by the sponsor. The causality and the seriousness may be upgraded (but never downgraded). Anonymized copies of documents providing useful information such as reports of further consultations, laboratory tests reports, reports of other examination aiding diagnosis may be asked for the event assessment. If the assessments of the investigator and the sponsor are different, both will be reported in the clinical study report (CSR).

In addition, the sponsor is responsible for determining whether an AE is **expected or unexpected**. An AE will be considered unexpected if the nature, severity, or frequency of the event is not consistent with the risk information previously described for the IMPs.

Independently of the regulatory obligations of the investigator, the sponsor must report the pharmacovigilance data and any new safety finding likely to affect the benefit /risk balance of the product, required in ICH Good Clinical Practice guidelines and local regulations, to the appropriate Authorities, to all the investigators involved and to the patients involved, through the investigators, as mentioned in [section 13.4](#).

The concerned Authorities will be notified as soon as possible by the sponsor of the DSMB recommendations if any, where relevant for the safety of patients (i.e. modification or termination of the study).

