3.4. Safety endpoints

All safety analyses will be performed in the SS (resp. DLTES for DLT analysis) by treatment dose level combination and overall. The treatment period is defined from first IMP intake up to last IMP intake date + (*) days.

(*) 30 days for AE and death analysis, 28 days for clinical laboratory evaluation, vital signs and clinical examination, centralized ECG and LVEF analysis.

Qualitative data will be presented in number and percentage of patients per class, while quantitative data will be presented in mean, SD, min and max, median, Q1 and Q3.

Calculation rules for expressions of safety endpoints, as well as general definitions (such as value prior to treatment / under treatment, analysable value, first and last IMP intake dates...), are provided in [Appendix 4.1](#).

Calculation rules for safety endpoints and other specific definitions are provided in [Appendix 4.2](#).

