3.4.2. Adverse events

Number of events, number and percentage of patients reporting at least one event, presented by primary SOC and PT (depending on the analysis), will be provided for SAEs over the study period and for treatment emergent adverse events (TEAEs).

TEAE will be described according to the seriousness, the worst grade, the severity, the relationship, the action taken regarding the IMP(s), the requirement of added therapy and the outcome.

Of note, the seriousness and the relationship with the IMPs (S64315 and/or azacitidine) of the adverse event are based on the investigator's opinion, but it includes also the sponsor decision to upgrade the seriousness and/or the relation to IMP(s) (the causal relationship will not be upgraded for EudraCT analyses).

The National Cancer Institute Common Terminology Criteria for Adverse Events Common Terminology Criteria for Adverse Events (NCI-CTCAE) classification version 5.0 will be used to classify all adverse events.

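### The SAP's derivation of azacitidine-related adverse events leaves out sponsor causality upgrades that its own section 3.4.2 includes, so these events can be under-counted

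*SAP*

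**What the plan says.** SAP section 3.4.2 describes how relationship is handled in the adverse event tables. It refers to "the relationship with the IMPs (S64315 and/or azacitidine) of the adverse event", so azacitidine is named. It bases relationship on the investigator's opinion and then adds that "it includes also the sponsor decision to upgrade the seriousness and/or the relation to IMP(s". One exception is stated: "the causal relationship will not be upgraded for EudraCT analyses".

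SAP section 3.4 points elsewhere for the derivations: "Calculation rules for safety endpoints and other specific definitions are provided in" Appendix 4.2. In that appendix, section 4.2.3.2 gives one rule per drug.

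- **S64315:** related events include "adverse events with relationship forced by the sponsor during the PV process", limited to events assessed as serious by the investigator or the sponsor, plus events that the investigator considered related.
- **Azacitidine:** "Adverse events related to azacitidine correspond to adverse events with relationship considered as" related in the investigator's assessment. There is no sponsor clause, and all other events fall into the not-related class.

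In the protocol, section 4.3.1 makes both drugs IMPs in Arm A. Section 8.8 treats a case as a suspected adverse drug reaction if either the investigator or the sponsor judges it related to the IMPs. On sponsor review, section 8.10 states: "The causality and the seriousness may be upgraded (but never downgraded"). It also requires the clinical study report to show both assessments where they differ.

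**The concern.** The two SAP sections give different answers for the same event. If the investigator calls an event unrelated to azacitidine and the sponsor upgrades it, the event is related under 3.4.2 and not related under 4.2.3.2. Both cannot be programmed, and section 3.4 sends the programmer to the appendix.

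The tables for the two drugs would then rest on different bases without saying so. Elsewhere 4.2.3.2 marks investigator-only definitions by name: it separates serious adverse events from serious adverse events by investigator assessment, and it labels the joint S64315-and-azacitidine definition as investigator assessment. The azacitidine definition carries no such label.

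What is at stake is attribution between the two drugs. Protocol section 2.3.4 expects overlapping toxicity, myelosuppression in particular. Relationship is one of the ways in which TEAEs are described, and efficacy is not analysed under this SAP, so the safety tables carry most of the report.

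**Working it through.** No figure in the plan is to be reproduced, so the check sets the two rules side by side and counts what each would capture.

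**Outcome of each rule for azacitidine (outside EudraCT output)**

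| Investigator | Sponsor | SAP 3.4.2 | SAP 4.2.3.2 |
|---|---|---|---|
| Related | Cannot downgrade | Related | Related |
| Not related | No upgrade | Not related | Not related |
| Not related | Upgraded to related | Related | Not related |

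Only the third row differs.

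**Count.** Let I be the events that the investigator called related to azacitidine. Let u be the events that the investigator called unrelated to azacitidine and the sponsor upgraded to azacitidine-related.

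- Section 3.4.2 counts I + u.
- Section 4.2.3.2 counts I.
- Difference: (I + u) − I = u.

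Protocol section 8.10 allows upgrades only, so u ≥ 0. The appendix count equals the 3.4.2 count if u = 0 and is lower whenever u ≥ 1. The documents do not give u.

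**What does not enter u.** Upgrades of seriousness alone, upgrades to S64315 alone, and upgrades of events that the investigator had already called azacitidine-related leave the difference unchanged. If the serious-event limit in the S64315 rule also applies to azacitidine, u contains serious events only. Protocol section 8.10 commits the sponsor to review causality for at least the SAEs, so non-serious upgrades are not ruled out.

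**Effect on a percentage.** One reclassified patient moves a patient-level percentage by 1/n, provided that the patient has no other azacitidine-related event in the same table row.

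- Protocol section 10.5.1 plans cohorts of 3 to 6 evaluable patients: 1/3 = 33 points, 1/6 = 17 points.
- With the planned maximum of 30 patients in dose escalation: 1/30 = 3.3 points.

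The Safety Set at a dose level can be larger than the evaluable cohort, and cohorts may exceed 6, so the dose-level figures are upper illustrations. SAP section 3.1 also limits percentages to dose levels with enough patients, so in the smallest cohorts the effect may appear only in the counts.

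**Outputs checked**

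- DLTs: taken from the investigator's record and not recalculated (SAP 4.2.3.1). Unaffected.
- EudraCT output: causality upgrades are excluded by 3.4.2 itself. Unaffected.
- Overall TEAE and SAE counts: defined by timing, worsening and seriousness, not by relationship. Unaffected.
- Joint relatedness to both drugs: labelled as investigator assessment, so not in conflict, but no version including sponsor upgrades exists.

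**The case against.** The best defence is that there is no true conflict. Section 3.4.2 is a summary note using loose terms, and the appendix gives one clear rule per drug. On this view 3.4.2 means that upgrades are included where they exist, and 4.2.3.2 says that they exist for S64315 only. This does not hold, because 3.4.2 names azacitidine and states a single exception, which is EudraCT and not azacitidine.

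A second defence is that the protocol itself singles out the test drug: the DLT definition requires relation to it, and the example of sponsor-judged causality in section 8.8 refers to its mechanism of action. That makes an intended asymmetry plausible, but the operative wording in 8.8 is about the IMPs, and neither document states that azacitidine is to be investigator-only.

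Third, protocol section 8.10 requires both assessments in the report when they differ. This is a real safeguard for disclosure. It does not correct the azacitidine-related table.

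Several limits stand. A reader might infer that azacitidine-related events are in fact under-counted; the documents do not show that the sponsor made any such upgrade. A reader might also take the shortfall to be all sponsor upgrades; only the third row of the table above contributes. Nor do the documents support a claim that the main safety results are distorted: the endpoints listed in SAP section 1.2 do not name relationship, the analysis is descriptive, and the report is abbreviated.

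**Conclusion.** The inconsistency is real, and the SAP is wrong as written: one of the two sections must change. Relative to 3.4.2, the appendix rule can only lower the number of azacitidine-related events, by u. The size of u is unknown and may be zero.

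The direction rests on the upgrade-only rule in protocol section 8.10 and on programming following the appendix, as SAP section 3.4 directs. The likely confinement to serious events rests on the limit written into the S64315 rule and is an inference for azacitidine. The consequence is limited to tables and listings of relatedness to azacitidine outside EudraCT. It merits correction because it costs little and otherwise leaves the two drugs attributed on different, unstated bases.

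**What to change.** In SAP section 4.2.3.2, give azacitidine the same clause as S64315: related if the investigator says so, or if the sponsor forces the relationship in the pharmacovigilance process for an event assessed as serious by the investigator or the sponsor. The serious-event limit must be carried over; without it a new asymmetry would arise. Keep the investigator-only version for EudraCT.

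If investigator-only attribution for azacitidine was intended, make three changes instead: restrict the upgrade statement in 3.4.2 to S64315, label the azacitidine table as investigator assessment, and report any differing sponsor assessment in the study report as protocol section 8.10 requires.

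The first option costs one SAP sentence and one derived flag and needs the sponsor's azacitidine assessment to be held per drug in the database, which the documents do not confirm. The second is a wording and labelling change, plus the reporting that the protocol already requires. Either is best settled before database lock.
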